### 3.9 Implications

These results suggest that adults with aMCI or AD may benefit from INI treatment. Compared with placebo, the lower dose of insulin improved delayed memory, and both insulin doses preserved caregiver-rated ability to carry out daily functions. General cognition as assessed with the ADAS-Cog, the primary outcome measure for the current trial, was also preserved by both doses of INI. In exploratory analyses, changes in CSF A $\beta$ 42 and tau/A $\beta$ 42 ratios were associated with cognitive and functional changes for insulin-treated participants. Placebo-assigned participants showed decreased CMRglc values in frontal, temporal, and parietal cortices as well as precuneus and cuneus over the 4-month period, whereas insulin-treated participants showed no decline. The longstanding FDG PET finding of posterior cingulate, precuneus and cuneus hypometabolism in AD has been hypothesized to be due to functional disconnection of the hippocampal formation, so enhanced metabolism and memory with INI may reflect enhanced hippocampal input to this region. Similarly there are strong connections between the posterior cingulate, precuneus, cuneus and prefrontal and superior temporal cortex (Cavanna and Trimble 2006), which may also be affected by INI. Finally, no treatment-related SAEs occurred. These promising results provide a strong rationale for the longer, larger, multi-site trial proposed in this application.

## 4.0 PRELIMINARY STUDY 2

A follow-up study has recently concluded and results have been published (Craft et al. JAMA Neurology, 2020).

**Objectives:** This study tested the effects of 40 International Units of intranasal insulin administered daily for 12 months, compared with placebo, on cognition, daily function and safety in adults with MCI or mild AD. Longer-term effects were examined in a six-month open-label extension offered to all participants. Safety and feasibility issues relating to the use of intranasal delivery devices were also evaluated. The trial is nearing completion; all participants have concluded the blinded phase.

**Methods:** Twenty-six sites enrolled 289 participants with MCI or mild AD in this randomized, double-blind, Phase II/III trial (NCT01767909). Adults 45 to 85 years of age with diagnoses of amnestic MCI

[figure not shown]
[figure not shown]
or AD (National Institute on Aging-Alzheimer's Association criteria) with Mini-Mental State Exam (MMSE) scores >19, Clinical Dementia Ratings (CDR) of 0.5 or 1, and delayed Logical Memory scores within a specified education-adjusted range were eligible. Participants with diabetes requiring medication were excluded, as were participants who had used insulin within one year of the screening visit. Participants were randomized on a 1:1 basis using a covariate-adaptive algorithm that weighted MMSE, apolipoprotein E-ε4 (APOE-ε4) allele carriage, study site, sex, and age based on previous work indicating these factors may impact treatment response. Participants received 40 International Units of insulin or insulin diluent placebo (Humulin R U-100 or insulin diluent, Eli Lilly, Indianapolis, USA) daily for 12 months. At the end of the 12-month blinded phase, all participants were offered open-label insulin treatment for 6 months. The primary outcome (Alzheimer's Disease Assessment Scale for Cognition-12/ADAS-Cog12) was administered at baseline and then at 3 month intervals. Secondary functional outcomes (Alzheimer's Disease Cooperative Study-Activities of Daily Living Scale for MCI; CDR Sum of Boxes) were assessed at 6 month intervals, as was a memory composite (Free and Cued Selective Reminding Test and Story Recall). Cerebrospinal fluid biomarkers (Aβ42 and Aβ42/tau ratio) and magnetic resonance imaging hippocampal and entorhinal cortex volumes were measured at baseline and after 12 months.

Device issues. Intranasal delivery device monitoring revealed no safety issues. However, for the first 49 participants, the delivery device had frequent malfunctions (i.e. failure to turn on) that impacted dosing reliability. At that time, a newly available device was introduced (Precision Olfactory Device/POD, Impel NeuroPharma, Seattle, USA) which was used by the remaining 240 participants with good reliability.

**Results:** Demographic characteristics of enrolled participants are presented in Table 1. Retention was excellent, with only 25 participants discontinuing treatment during the blinded phase, and 15 also discontinuing study visits during the blinded phase. Quarterly DSMB reviews did not detect any safety issues and approved unmodified continuation of the trial.

Data from the subgroup of participants who used the POD were analyzed separately from the ViaNase group. The primary analysis of the POD group showed was negative; no difference in ADAS-Cog12 scores were observed after 12 months of INI treatment compared with placebo (Fig.1). In contrast, analysis of the ViaNase group showed beneficial effects of insulin compared with placebo; the effect was significant at 6 months ( $p<0.01$ ), and persisted at 12 months ( $p=0.09$ ; Fig. 2).

Table 1. Baseline Participant Characteristics	
N (F/M)	289 (134 / 155)
Age (years)	70.95 ± 7.1
Diagnosis (MCI/AD)	105 / 184
MMSE	24.8 ± 2.7
Logical Memory	2.1 ± 2.7
APOE (ε4+/ε4-)	193 / 96

**Fig. 1**

**Implication:** These results suggest that the two delivery devices may be providing different doses of insulin to the CNS. The ViaNase device results are consistent with multiple previous studies. The POD had not been used previously in clinical trials with insulin, and thus was relatively untested in terms of delivery efficacy, although modeling in organoid nasal cavities was conducted to verify that the target amount of insulin was dispersed to the target location in the nasal cavity. These divergent results raise the possibility that specific characteristics of the device can affect delivery. Any future studies of intranasal insulin will need to utilize devices that have been demonstrated to effectively deliver insulin to the CNS. A study currently in progress compared delivery of two doses of insulin with 2 devices in order to provide supportive evidence for future trials.

[figure not shown]
## 5.0 PRELIMINARY STUDY 3

**Objectives:** The Device Delivery Study compared whether delivery of 20 or 40 IU of insulin with the Aptar VP7 or CPS devices raised insulin acutely in CSF.

**Methods:** The study consists of a single site, randomized, double-blind trial comparing the acute effects of INI (20 or 40 International Units) delivered with the Aptar CPS or VP7 devices on CSF insulin levels, AD biomarkers and memory. At study entry, participants were randomized to the CPS or VP7 device. They were then randomized to receive either a 20 or 40 IU dose of insulin first, and the other dose on a second visit. Participants who were cognitively normal or who had aMCI (n=10) were enrolled. The primary outcome measure consisted of CSF insulin levels. Secondary measures included a memory test and CSF biomarker levels.

Two lumbar punctures were performed in the morning after a minimum 8-hour overnight fast at least a week apart. After insertion of the spinal catheter, blood and CSF was collected immediately. Insulin (20 or 40 IU) was then be administered, and additional CSF and blood was collected at 10 and 20 minutes following administration, after which the spinal catheter was withdrawn.

**Results:** Although the study is ongoing, preliminary analyses have been conducted to inform the design of the current trial. Change in CSF insulin from baseline values are shown below for individual participants (left) using the VP7 and CPS devices to administer 20 IU (Dose 1) and 40 IU (Dose 2). Mean change for the groups is shown on the right.

Results showed that the VP7 device did not reliably increase CSF insulin levels, with only one participant in the 40 IU dose showing elevations after administration. More reliable elevations were demonstrated with the CPS device, particularly for the 40 IU dose. All five participants showed increased CSF insulin after administration, and the average change was significant. Based on these

**Fig. 2**

data, the CPS device has been selected for this pilot trial, as has the 40 IU dose.

### **5.1 Rationale for Dosage Selection**

The dosage of insulin selected (40 International Units INI q.i.d.) has been used in multiple prior studies with positive results. The dosage of empa (10 mg q.d.) is also standard and has been used in previous large trials (EMPA-REG-OUTCOME).

### **5.2 Rationale for Primary and Secondary Outcome Measures**

Because no published study has examined the safety of empagliflozin in adults with Alzheimer's disease or in combination with intranasal insulin, the proposed study specifies safety, defined as number of treatment-related adverse events, as the primary outcome..

Regarding secondary measures, in previous studies intranasal insulin acutely improved cognitive performance and affected CSF levels of AD biomarkers as well as MRI measures of vascular integrity (Reger et al. 2008; Craft et al. 2012; Kellar et al. 2021). Thus examining effects on these measures will provide information to be used in the design of a future Phase II trial.

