PRIMARY OBJECTIVE	We will test the hypothesis that 1 month of treatment with INI (40 IU q.i.d.), with the SGLT2i empagliflozin (empa; 10 mg q.d.), and with combined insulin plus empagliflozin (INI+empa) will result in safety profiles (number of treatment-related serious adverse events/primary outcome) that are similar to placebo.
SECONDARY OBJECTIVES	We will determine the effects of singular and combined therapy on AD cerebrospinal fluid biomarkers, cerebral blood flow (CBF) and cognition.
PRIMARY OUTCOME MEASURE	Number of treatment-related serious adverse events
SECONDARY OUTCOME MEASURES	PACC5, ADAS-Cog14, CSF A $\beta$ 40, A $\beta$ 42, total tau, and phospho-tau 181, whole brain CBF
STUDY DESIGN	Single-site, double-blind study
SAMPLE SIZE	n=60
SUMMARY OF KEY ELIGIBILITY CRITERIA	
 
Cognitively normal with positive amyloid (amyloid PET SUVR>1.21, CSF A<math>\beta</math>42<600 pg/ml)
 
Diagnosis of amnestic mild cognitive impairment (MCI) or early AD (CDR 0.5 or 1, MMSE>21)
 
Age: 55 to 85 years (inclusive)
 

DRUG DOSAGE & FORMULATION	40 International Units Humulin® R U-100 (Eli Lilly, Inc.) q.i.d.; empagliflozin (10 mg q.d.)
DURATION OF PARTICIPATION	8 weeks (4 weeks on active treatment)
PLACEBO	Insulin diluent (Eli Lilly, Inc.); cellulose capsule

ROUTE OF ADMINISTRATION	Intranasal (insulin); oral (empagliflozin)
PROCEDURES	Physical and neurological exam, nasal examination, cognitive testing, magnetic resonance imaging (MRI), continuous glucose monitoring, actigraphic sleep assessment, lumbar puncture, vitals, clinical labs, CSF and blood analysis and banking and APOE genotyping.

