### **1.1 Primary Aim**

We will test the hypothesis that 4 months of treatment with INI (40 IU q.i.d.), with the SGLT2i empagliflozin (empa; 10 mg q.d.), and with combined insulin plus empagliflozin (INI+empa) will result in safety profiles (number of treatment-related serious adverse events/primary outcome) that are similar to placebo.

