## **6.0 STUDY OVERVIEW**

The study will consist of a single site, randomized, double-blind trial comparing the effects of 4 weeks of INI (40 International Units q.i.d.), empa (10 mg q.d.) and combined INI and empa compared with placebo on CSF biomarkers and cognition. At study entry, participants will be randomized to one of 4 conditions: INI, empa, INI+empa, placebo. Participants who are cognitively normal but have abnormal elevations of brain amyloid (n=20) or who have MCI or early AD (n=40) will be enrolled. The primary outcome measure will consist of safety (treatment-related serious adverse events). Secondary measures will consist of CSF biomarkers, cognition, and cerebral blood flow. Exploratory measures will include continuous glucose levels and sleep quality as assessed with actigraphy.

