## **12.0 STATISTICAL PLAN**

Statistical analyses will be conducted by the ADRC Biostatistics Core. To address the Primary Aim, number of treatment-related SAEs will be subjected to a repeated measures analysis of variance with group and time as the repeated measures. Secondary analyses will examine the effect of diagnostic status (cognitively normal vs. MCI/AD). Secondary analyses will also examine treatment-related differences for other CSF and plasma biomarkers, cognitive scores, and whole brain cerebral blood flow.

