### **20.4 Data and Safety Monitoring Plan**

The principal investigator and study clinician(s) will be responsible for the overall monitoring of the data and safety of study participants, with assistance by members of the study staff. Participants will be screened at the beginning of the study and will be monitored carefully at each study visit. Participants will be queried for serious adverse events (SAEs) and selected AEs (those temporally related to study procedures) at each study visit. All SAEs and selected AEs will be recorded on an AE case report form. Based on the nature of the AE, study clinicians will determine the severity of the event and association with the study. All serious adverse events will be reported. Serious adverse events are defined as events that are (1) life-threatening or fatal, (2) result in severe or permanent disability, or (3) require hospitalization. SAEs will be reported to the IRB within 7 days of investigator

knowledge of the event if they are related and unanticipated (i.e. if they qualify as an unanticipated problem). All serious adverse events will be followed until resolution, or 90 days after study participation has been terminated.

"Severity" of events will be graded according to the following guidelines:

1. Mild: The participant is aware of, but can easily tolerate, the event
2. Moderate: The discomfort of the event is severe enough to interfere with some usual activities
3. Severe: The participant is incapacitated, and unable to perform most or all usual activities

The "study-relatedness" will be assigned according to the following guidelines:

1. Definitely Related: The reaction follows a reasonable temporal sequence and is known to be an effect of participation or a procedure
2. Possibly Related: The reaction follows a reasonable temporal sequence, and current medical knowledge does not preclude a relationship between participation or procedure and the event.
3. Unlikely: Little evidence to suggest a causal relationship (e.g. the event did not occur within a reasonable time after administration of the trial medication) or another reasonable explanation for the event (e.g. another clinical condition or other concomitant treatment).
4. Definitely Unrelated: Current medical knowledge precludes a causal relationship between participation or procedure and the event or the cause of the reaction is known to be other than participation or procedure.

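### Section 20.4 restricts adverse event recording to SAEs and procedure-timed events, contradicting Sections 16.1 and 10.1, so non-serious drug reactions could go unrecorded

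*Combined protocol and SAP*

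**What the plan says.** **Recording scope.** Section 20.4 (Data and Safety Monitoring Plan) states: "Participants will be queried for serious adverse events (SAEs) and selected AEs (those temporally related to study procedures) at each study visit". It then adds: "All SAEs and selected AEs will be recorded on an AE case report form". Section 16.1 sets a different rule: every adverse event, whether or not the clinician judges it drug-related, goes into the medical record and onto the electronic AE form. Section 10.1 has any occurrence reviewed and documented at each visit. The visit descriptions in Sections 8.1 to 8.7 and the adverse event row of Table 4 cover all six visits and the phone call. They set no limit, but they also state no scope.

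**Primary outcome wording.** Section 5.2 reads: "the proposed study specifies safety, defined as number of treatment-related adverse events, as the primary outcome". The synopsis, in both its objective and its outcome line, gives the "number of treatment-related serious adverse events". Section 1.1 refers to "safety profiles (number of treatment-related serious adverse events/primary outcome) that are similar to placebo", Section 6.0 also specifies serious events, and Section 12.0 says that the "number of treatment-related SAEs will be subjected to a repeated measures analysis of variance".

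**Relatedness.** Section 16.1 requires each event to be judged for a causal link to the study drug but supplies no grades. Section 20.4 supplies four grades of study-relatedness: definitely related, possibly related, unlikely and definitely unrelated. Three of them are worded around participation or procedure. Possibly related, for example, applies when "current medical knowledge does not preclude a relationship between participation or procedure and the event". Only the unlikely grade mentions the trial medication.

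**The concern.** This is a pilot whose stated purpose is safety. Section 5.2 gives as its reason that empagliflozin has no published safety study in Alzheimer's disease or in combination with intranasal insulin. Non-serious reactions are therefore part of what the trial exists to describe. A rule that ties recording to the timing of study procedures selects events on something other than drug exposure. The reactions most likely to be lost are those that arise at home between visits. Section 13.1 (Safety of empagliflozin) names genital yeast infection and frequent urination, and neither need follow a lumbar puncture, scan or sensor placement. If such events are more common on active treatment, dropping them makes the arms look more alike than they are.

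**Working it through.** The plan gives no figure for this point, so the check compares passages and works out the direction of any bias.

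**Step 1. The recording rules side by side.**

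| Place | What is recorded | Scope stated? |
|---|---|---|
| Section 20.4 | SAEs, plus adverse events close in time to study procedures | Yes, restricted |
| Section 16.1 | All adverse events, drug-related or not | Yes, unrestricted |
| Section 10.1 | Any occurrence | Yes, unrestricted |
| Sections 8.1 to 8.7, Table 4 | Adverse events | No |

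The direct contradiction is between the first row and the next two. The last row fits either rule.

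**Step 2. A test case.** Take a non-serious genital infection that begins at home midway between visits. Under 16.1 and 10.1 it is recorded. Under 20.4 it is neither an SAE nor close in time to a visit procedure, so it need not be asked about or entered. It would qualify only if dosing counts as a study procedure. Section 15.0 has each participant taking four intranasal doses and one oral dose a day. On that reading nearly every event in the treatment period falls near a procedure, and the restriction to selected events selects almost nothing.

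**Step 3. Direction of the bias.** Let *c* be the mean number of procedure-timed events per person and *b* the mean number of background events away from procedures, both the same in every arm. Let *d* be the extra drug-caused, non-serious events away from procedures on an active arm. Let *f* be the fraction of events away from procedures that is actually recorded, the same in every arm.

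- Active arm recorded: *c* + *f*(*b* + *d*)
- Placebo recorded: *c* + *f b*
- Difference: *f d*

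With full recording (16.1), *f* = 1 and the difference is *d*. With 20.4 applied strictly, *f* = 0 and the difference is 0. Mixed practice falls between. The bias runs towards similarity with placebo. Its size depends on *d* and *f*, and the documents give neither.

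**Step 4. Does it reach the primary outcome?** Section 20.4 queries and records all SAEs. Section 16.1 records all adverse events and evaluates each for seriousness. An SAE is captured under both, so the SAE count does not depend on which rule is followed.

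**Step 5. Outcome wording.** Statements that specify serious events: synopsis objective, synopsis outcome line, 1.1, 6.0 and 12.0, which makes 5. Statements that omit the word: 5.2, which makes 1.

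**Step 6. Attribution.** Relatedness grades defined: 4. Places that map grades to treatment-related: 0. At both lumbar puncture visits (Sections 8.3 and 8.7), insulin is given while the spinal catheter is in place. An event that day follows drug and procedure alike, so timing alone cannot separate them.

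**The case against.** The best defence is that Section 16.1 is the dedicated adverse event section and is explicit, so a trained coordinator would follow it, and that study procedures can be read to include dosing. Neither settles the matter. Nothing gives 16.1 precedence over 20.4, which is the data and safety monitoring plan, and the wide reading leaves the restriction with almost nothing to do.

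Other parts of the defence do stand, and they block several stronger readings.

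- *That the primary outcome would be under-counted.* It would not, because SAEs are recorded under both rules. Only the 5.2 wording would expose the primary outcome, and that is one outlier in a rationale paragraph, probably a dropped word. An analyst working from 12.0 would not be misled.
- *That Table 4 and the visit lists contradict 20.4.* They state no scope, so they conflict at most by implication.
- *That treatment-related has no meaning in the protocol.* Its natural reading is the 16.1 judgement about study drug, under which an SAE caused by the puncture itself is not treatment-related. What is missing is mainly the grade cut-off.
- *That classification of puncture complications could readily swing the result.* Section 13.5 puts infection, nerve damage and bleeding at much less than 1%. Taking 1% as a ceiling gives 60 × 0.01 = 0.6 events per 60 participants or, if assumed to apply per puncture, 120 × 0.01 = 1.2. The section does not say that all of these would be serious, and every arm has both punctures.
- *That nasal reactions would be missed.* Table 4 schedules nasal examinations at five of the six visits, so this is a weak example. Volume depletion is weak too, because Section 13.1 (Safety of empagliflozin) separately promises hypotension monitoring at visits and on calls.

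**Conclusion.** The recording rule in Section 20.4 is wrong as written and should be fixed. It directly contradicts 16.1 and 10.1 and, if followed, could remove non-serious drug reactions from the safety data. The effect is confined to the non-serious comparison between arms. Its direction is towards no difference, assuming that the lost events are more frequent on active treatment and that recording practice is the same across arms. Its size cannot be calculated from the documents.

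The SAE primary outcome is not affected, provided that the same events are classed as serious under both sections; 20.4 lists its own criteria where 17.1 refers to federal regulation. The Section 5.2 wording is an editorial correction. The undefined grade cut-off is a clarification, worth making because the expected count is small and the 20.4 scale mixes participation with procedure.

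**What to change.** 1. Amend Section 20.4 so that all adverse events, serious or not, are queried at each contact and recorded on the AE form, as 16.1 and 10.1 already require. Delete the restriction to selected events.
2. Add to Section 12.0 a table of all-cause adverse events by randomised arm. It needs no causality judgement.
3. Correct Section 5.2 to match the five statements of treatment-related serious adverse events.
4. State, before unblinding, that treatment-related means the 16.1 judgement of relationship to study drug, and name the grades that count, including whether possibly related does.

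The cost is protocol and form wording, plus modest extra data entry at visits and a call already scheduled. No new assessments are needed.
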